11.1.4. General Guidelines for AE Reporting

Collection of AEs and SAEs will commence from the time the subject signs the informed consent to participate in the study and continue until the end of the study. All AEs must be entered on the corresponding pages of the CRF, regardless of causality or severity. AEs include new AEs, worsening baseline conditions, clinically significant laboratory findings, disease-related signs and symptoms that were not present at baseline, and any events or findings that the Investigator feels are clinically significant.

Information collected concerning AEs will include the following:

- Name of the event (whenever possible, diagnosis or single syndrome should be reported instead of symptoms)
- Start date
- Stop date
- Severity (i.e., mild, moderate, severe, potentially life-threatening, death)

- Relationship to study treatment (related, not related)
- Action taken with the study treatment (dose not changed, drug interrupted, drug withdrawn, not applicable, unknown)
- Outcome (recovered/resolved, recovering/resolving, not recovered/not resolved, resolved with sequelae, fatal, unknown)
- Seriousness of event (SAE or non-SAE)

Pretreatment AEs are defined as any untoward medical occurrence in a clinical investigation subject who has signed informed consent to participate in a study but prior to administration of any study medication; it does not necessarily have to have a causal relationship with study participation. Treatment-emergent adverse events (TEAEs) are defined as AEs that developed or worsened during the treatment-emergent period. The treatment-emergent period is from first administration of study treatment to end of the follow-up period. Pre-existing conditions (present at the time of signing of informed consent) are considered concurrent medical conditions and should not be recorded as AEs unless they worsen in severity or increase in frequency. Screening evaluation findings (e.g., laboratory tests, ECG, etc.) should not be recorded as Pretreatment AEs unless related to study procedures.

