Prior (within the previous 30 days and with stop dates prior to first administration of study treatment) and concomitant (ongoing or with stop dates on or after first administration of study treatment) medications will be presented in a by-subject listing for each treatment group, medications used as rescue treatment will be flagged. Medications will be coded using World Health Organization Drug Dictionary (WHO-DD) version March 2020 terminology.

For the determination of prior vs. concomitant medications, the following rules regarding the stop date will be applied:

- If only year was recorded, and it is before Baseline, it is a prior medication; if year is same or after Baseline, it is assumed to be a concomitant medication.
- If day is missing, but month and year are before Baseline, it is a prior medication; if month and year are the same as Baseline, it is assumed to be a concomitant medication; if month and year are after Baseline, it is a concomitant medication.
- If start date is after Baseline, it is a concomitant medication regardless.

Additionally, concomitant medications and medication used as rescue treatment will be summarized by treatment group, by the number and percentage of subjects taking each medication, classified using WHO-DD Anatomical Therapeutic Chemical (ATC) classes and preferred terms (PT).

7. Subject Accountability

A. Disposition

The numbers of subjects screened, who screen fail (along with the reason), who were randomized, completed the study, and discontinued, along with reasons for discontinuation, will be tabulated using frequencies and percentages, overall and by treatment group, as well as pooled CBP-201 group. The number of subjects in

each analysis population and who were excluded from PPS (overall and by reason for exclusion), will be summarized as well.

Due to the outbreak of COVID-19 pandemic, COVID-19 related subject disposition events will be further summarized per FDA Guidance on Conduct of Clinical Trials of Medical Products during COVID-19 Public Health Emergency (thereinafter referred to as FDA COVID-19 Guidance)¹, for the following:

- Number of subjects discontinued from treatment or study for reasons related to COVID-19
- At each scheduled visit:
 - Number of subjects with visits missed due to COVID-19
 - Number of subjects with any efficacy assessments not done due to COVID-19

B. Protocol Deviations and Population Inclusions

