All AEs will be coded using MedDRA version 24.0 or higher. A treatment-emergent AE (TEAE) is defined as any AE that occurs or worsens after initiation of study treatment.

The duration in days of each AE will be calculated as (resolution date of AE – onset date of AE + 1). For the determination of TEAEs and calculation of durations for AD flares, the following rules regarding partial dates will be applied:

- If only the day is missing for a start date, the 1st of the month will be imputed. If the new estimated date falls before the date of first dose, while the known month and year match the month and year of the first dose, the date of first dose will be used as the new estimated date. The AE will be considered as a TEAE.
- If only the day is missing for an end date, the last day of the month will be imputed. If the new estimated date falls after the date of last study visit, the date of last study visit will be used as the new estimated date.
- If both the day and the month are missing for a start date or end date, no imputation will be used, and the duration will not be calculated. However, if the year of start is the same or greater than the year of the first dose date, the AE will be considered as treatment emergent.

- If the start date or end date is completely missing, duration will not be calculated. However, an event with completely missing start date will be considered as treatment emergent.

An overall summary of AEs will be presented by treatment and overall. The summary will include the total number of events, frequency counts and percentages with:

- All AEs
- TEAEs
- Treatment-emergent Serious Adverse Events (SAEs)
- Treatment-related TEAEs
- Treatment-related treatment-emergent SAEs
- TEAEs leading to study drug discontinuation
- Injection site reactions
- AEs of Special Interest (AESIs): conjunctivitis, keratitis and other ophthalmic events evaluated by an ophthalmologist.

Summaries of the incidence of TEAEs will be displayed by treatment according to the following:

- All TEAEs by SOC in descending order of frequency (in the sequence of all subjects, all active treatments, CBP-201 3000 mg [300 mg Q2W] group) and PT in the same order of frequency
- All TEAEs by SOC, PT, and maximum severity (1 mild, 2 moderate, 3 severe, 4 life-threatening, 5 death)
- All TEAEs by SOC, PT, and maximum causality (not related, related) to study treatment
- All serious TEAEs by SOC and PT
- All AESI by SOC and PT

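### The partial-date rules in SAP 9.B make an adverse event treatment-emergent even when its recorded end date shows that it was over before the first dose

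*SAP*

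**What the plan says.** SAP 9.B defines the category first: "A treatment-emergent AE (TEAE) is defined as any AE that occurs or worsens after initiation of study treatment". It then gives the handling of incomplete dates, with a stated double purpose: "For the determination of TEAEs and calculation of durations for AD flares, the following rules regarding partial dates will be applied".

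Three of the rules confer treatment-emergent status:

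- **Start day missing.** The first of the month is imputed. If that falls before the first dose but in the same month and year, "the date of first dose will be used as the new estimated date. The AE will be considered as a TEAE".
- **Start day and month missing.** Nothing is imputed and no duration is calculated, but the AE is treatment-emergent if "the year of start is the same or greater than the year of the first dose date".
- **Start date absent.** No duration is calculated, but "an event with completely missing start date will be considered as treatment emergent".

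The only imputation rule for the end of an event completes it: "If only the day is missing for an end date, the last day of the month will be imputed", capped at the last study visit. It plays no part in deciding treatment-emergent status. Duration is the end date minus the onset date plus 1, with no minimum.

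Protocol 11.1.4 states: "Collection of AEs and SAEs will commence from the time the subject signs the informed consent". The same section defines events after consent and before any study medication as pretreatment AEs, and starts the treatment-emergent period at the first dose. Screening lasts up to 45 days (Protocol 7.1.1).

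SAP 8.D records AD flares as AEs, counts them by onset date from baseline to Week 16, and adds up their durations within a subject.

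**The concern.** Treating an event of uncertain timing as treatment-emergent is a sensible default. Here the default is also applied where nothing is uncertain. If the recorded end date precedes the first dose, the event did not occur or worsen on treatment, however little is known about its start. The rule nevertheless places it in the TEAE tables.

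The missing-day rule adds a second fault. By moving the onset to the first-dose date it can put the start of an event after its recorded end. For most AEs that is an implausible line in a listing. For an AD flare it reaches two efficacy summaries and pushes them in opposite directions: the flare count goes up by one, and the subject's flare-day total goes down.

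**Working it through.** The plan gives no figure to reproduce on this point, so the check applies the rules as written.

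**1. Can such an event be in the data?** Yes. AE collection begins at consent, and screening can run for 45 days before Day 1. I found no end-date check, minimum duration or overriding statement in either document.

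**2. Missing-day rule, worked example (illustrative dates).** First dose 20 March; AE start recorded as March only; AE end 10 March.

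- Imputed start: 1 March. This is before the first dose and in the same month, so it is moved to 20 March.
- Status: TEAE.
- Duration: 10 − 20 + 1 = −9 days.

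Had the onset stayed at 1 March, the duration would be 10 − 1 + 1 = 10 days and the event would be a pretreatment AE.

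**3. Missing-day rule in general.** Let the first dose fall on day f of a month and let the AE end on day e of the same month, with e < f. The rule sets the onset to f, so duration = e − f + 1. This can never exceed 0. It is 0 when the event ended the day before dosing and negative otherwise.

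Listing every pair (f, e) over an assumed 365-day calendar:

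- A month of d days gives d(d − 1)/2 pairs: 7 × 465 + 4 × 435 + 378 = 5,373.
- Duration 0: 365 − 12 = 353 pairs.
- Duration negative: 5,373 − 353 = 5,020 pairs.
- Duration positive: none.
- Minimum: f = 31, e = 1 gives 1 − 31 + 1 = −29 days.

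All 5,373 would be TEAEs. This count shows how the rule behaves; it is not a forecast of how often the case arises.

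**4. Year-only rule.** For a first dose on 15 February, 45 days earlier is 1 January. So for any first dose on or after 15 February the whole screening window lies in the first-dose year. Every screening AE with a year-only start is then a TEAE, including one with a complete end date before dosing. No duration is calculated.

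**5. Absent start date.** The AE is always a TEAE, whatever its end date. No duration is calculated.

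**6. Both days missing.** If start and end are each recorded as March only, the end becomes 31 March and the duration is 31 − 20 + 1 = 12 days. It is not negative, and the timing is truly unknown, so the default is reasonable.

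**7. Effect on a flare.** Suppose the AE in step 2 is a flare, and the same subject has a real on-treatment flare of 10 days (an assumed length). Using the imputed onset in the count as well, the subject has 2 flares instead of 1, and 10 + (−9) = 1 flare day instead of 10.

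**The case against.** The best defence is that little turns on this. SAP section 9 makes no formal safety comparisons, SAP 8.D summarises the flare endpoints descriptively, the rule is identical in all arms, and the AE listing shows onset and end dates, so an odd case could be spotted. Sites also ask about AEs at Baseline and entries are monitored, so partial start dates may be few or none. All of that stands, and it limits the point to a small correction. It does not make the rule right: the text says outright that such an AE is a TEAE.

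Four stronger readings are tempting, and the documents do not support them.

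- **A large error rate.** With AE starts spread uniformly over 45 days and first doses spread uniformly over the year, about 33% of screening AEs lacking only the day, about 94% of those with only a year, and all of those with no start date would be flagged. A reader might take these as misclassification rates. They are not, because they ignore end dates. For an event that was ongoing or had an unknown end, the flag is a reasonable default.
- **Screening flares are likely because of the topical washout.** Neither document says so. Flares are identified by use of topical corticosteroids, which are excluded in the week before Baseline. Subjects must still have EASI of at least 16 and IGA of at least 3 at Baseline, so a washout flare is more plausibly still present on Day 1 than resolved. A flare treated and resolved earlier in screening remains possible.
- **The related-TEAE and special-interest tables are inflated.** Relatedness is the investigator's call, and the definition of not related in Protocol 11.1.1 fits an event that ended before dosing. For events of special interest, the line in the SAP's overall AE summary carries no treatment-emergent qualifier, so its dependence on this rule is unclear.
- **SAP 9.B contradicts the medication rule in SAP 6.C.** That rule identifies prior medications as those "with stop dates prior to first administration of study treatment", but it defines a different thing. It shows that the SAP uses stop dates elsewhere; it is a contrast, not a contradiction.

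**Conclusion.** The rules are wrong as written, within a narrow scope. An AE with a partial or missing start date that meets one of the three rules, and whose end date shows that it was over before the first dose, is classed as a TEAE. That contradicts the TEAE definition in SAP 9.B and the pretreatment category in Protocol 11.1.4. AEs with complete start dates are not touched.

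Zero or negative durations, and shifted flare onsets, come only from the missing-day rule combined with an end date known to the day and before dosing. The other two rules misclassify status but produce no duration. The flare effect further requires a flare recorded as an AE in screening and resolved before Day 1, and it assumes that the flare count takes the same imputed onset date as the duration.

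The documents do not say how many AEs have incomplete start dates. The number affected is probably small and could be zero. The primary analysis is not involved.

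**What to change.** Add a condition to SAP 9.B ahead of the start-date rules: an AE whose known or partial end date establishes that it ended before the first dose is a pretreatment AE and not a TEAE, and an imputed start date may not be later than a known end date. State that the same condition governs AD-flare onset and duration in SAP 8.D.

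Keep the treatment-emergent default for events that are ongoing or whose end date does not settle the matter.

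The cost is about one sentence in the SAP and one line of derivation code. No new data are needed.

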150 mg group, by 52.8% in the 300 mg group versus 22.8% in the placebo group. P-NRS response rates (>3-point decrease) were greater for the 150 mg (50%, 4/8) and 300 mg groups (57%, 4/7) versus the placebo group (25%, 2/8) on Day 29.

Safety: CBP-201 appeared to be safe and well-tolerated when administered to male and female adult patients with moderate to severe AD, at SC doses of 75 mg, 150 mg, and 300 mg. These conclusions were based on the following findings from 23 patients in the pooled CBP-201 group who received at least one dose of CBP-201 and 8 of 8 patients in the placebo group.

- There were no SAEs, life-threatening TEAEs, or deaths reported on study.
- There were no TEAEs leading to the discontinuation from the study.
- The majority of TEAEs were mild. The number and severity of TEAEs and treatment related TEAEs did not increase with increasing CBP-201 dose level. Of 51 TEAEs reported across the pooled CBP-201 group, 9 events were deemed by the Investigator to be related to study drug, and 3 of 11 TEAEs in the placebo group were deemed related to placebo treatment. There was no treatment related severe TEAEs reported.
- The most common Adverse Events (AE) during the study were exacerbation of AD (26.1% in the combined CBP-201 group and 37.5% in placebo group), headache, and upper respiratory tract infection.
- By dose across the CBP-201 treatment groups, there were no apparent differences between the different dosing groups in terms of study treatment related TEAEs.
- There were no clinically significant injection site reactions that were reported as AEs
- There were no clinically significant and/or study drug-related changes in vital signs, ECG parameters, or physical examination findings.
- Immunogenicity assay results showed 5 of 23 patients (21.7%) had a treatment-induced positive response for ADA with very low titration. Overall, the immunogenicity of CBP 201 varied inversely with the CBP-201 dose, with the incidence of treatment-induced ADA positive response observed to decrease with greater CBP 201 doses.

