7.1.2.3. AD Flares and Rescue Treatment

AD is a chronic relapsing skin condition that is characterized by periods of disease flare or escalation of symptoms. Many flare definitions rely on a physician's assessment or subject report (38), however a relatively recent review suggests that an escalation of treatment (or rescue) and days of topical corticosteroid (TCS) use were good indicators of flare and flare duration (39). Therefore, when an AD flare occurs, its onset and duration will be documented as an AE by the location(s) of flare involvement. If the Investigator determines that the flare is severe enough to merit "rescue" treatment, document the choice of TCS and

instructions for its use and the duration of such permitted rescue TCS treatment. The subject need not be discontinued in this situation. Permitted TCS medications to treat AD flares may include the following:

- Cream based preparations or lotion in hair bearing areas
- Low to moderate potency TCS (WHO classification VII-IV) equivalent to class VII – IV according to the U.S classification are allowed. The TCS regimen will be adjusted to the flare activity and tolerability by the subject, and stopped when lesions are cleared.
 - Examples:
 - Methylprednisolone acetate 0.1%
 - Mometasone furoate 0.1%
 - Betamethasone valerate cream 0.1%
- If possible, Investigators should attempt to limit the first step of rescue therapy to permitted TCS rescue treatment and escalate to systemic medications only for patients who do not respond adequately after the treatment of permitted TCS.

If a patient receives any other rescue treatment including other topical rescue treatments (apart from permitted TCS and bland emollients), systemic corticosteroids or nonsteroidal systemic immunosuppressive/immunomodulating drugs (cyclosporine, methotrexate, mycophenolate mofetil, azathioprine, Janus kinase inhibitors, biologic agents, etc), the study treatment will be immediately discontinued. In this situation, subjects should remain in the study and continue with study procedures (complete the schedule of study visits and assessments) but will not receive additional study drug administration.

Investigators should make every attempt to conduct efficacy and safety assessments (eg, disease severity scores, safety labs) immediately before administering any rescue treatment. An unscheduled visit may be used for this purpose if necessary.

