13.6.2. Analysis for secondary efficacy endpoint

The secondary efficacy endpoints are as follows:

- IGA (0-1): Proportion of subjects with both IGA score 0 to 1 and a reduction of ≥ 2 points at Week 16
- EASI:
 - EASI-50: Proportion of subjects achieving $\geq 50\%$ reduction of EASI score from Baseline at W16
 - EASI-75: Proportion of subjects achieving $\geq 75\%$ reduction of EASI from Baseline at W16
 - EASI-90: Proportion of subjects achieving $\geq 90\%$ reduction of EASI from Baseline to W16
- Change from baseline to Week 16 in weekly average of PP-NRS
- Number of AD flares from Baseline through W16
- Number of days with AD flare from Baseline through W16

For categorical secondary efficacy endpoints, counts, percentage, and confidence interval obtained based on the Clopper-Pearson method will be presented for each CBP-201 regimen and placebo, respectively. For quantitative secondary efficacy endpoints, the method for statistical analysis is similar to those for primary efficacy endpoints.

Proportion of subjects achieving IGA (0-1), and proportion of subjects achieving EASI-50, EASI-75, or EASI-90 in the EASI score will be plotted by treatment and scheduled time. Mean change (\pm SD) from baseline for P-NRS will be plotted by treatment and scheduled time.

For the secondary efficacy endpoints, summary statistics will be provided by treatment group. The clopper-pearson confidence interval will also be provided for endpoints of proportions. No formal statistical comparison will be performed.

In this study, subjects are permitted to take TCS treatment (rescue) for AD flares. It is expected subjects randomized to placebo arm will require TCS medication more often or for longer periods.

All other details for efficacy analyses will be handled as discussed in the Study's SAP.

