For binary secondary efficacy endpoints (IGA response, EASI-50, 75, 90 response), counts, percentage, and 95% CIs obtained based on the Clopper-Pearson method (SAS PROC FREQ PROCEDURE, exact binomial) will be presented for each CBP-201 regimen and placebo, respectively, based on FAS; p-value for pairwise comparisons for each CBP-201 group vs. placebo will also be presented in an exploratory manner. For responder endpoints, missing value will be imputed using NRI.

For change from baseline to Week 16 in weekly average PP-NRS, the method for statistical analysis is similar as described above for primary efficacy endpoint, with replacement of PP-NRS by EASI in the model, using LOCF for all visits based on FAS and also WOCF at Week 16 as sensitivity analysis..

Proportion of subjects achieving IGA (0-1), and proportion of subjects achieving EASI-50, EASI-75, or EASI-90 in the EASI score will be plotted by treatment and scheduled visits using bar plots. Mean reduction (\pm SD) from baseline for PP-NRS will be plotted by treatment and study week.

D. Other Efficacy Outcome Analyses

Binary endpoints will be analyzed using similar method as described above for secondary efficacy endpoints:

- EASI-50/EASI-75/EASI-90 at Week 20
- EASI-100 at Week 16 and Week 20
- IGA Score 0
- Proportion of subjects achieving ≥ 2 -point improvement in IGA from Baseline to Week 16

- Proportion of subjects achieving ≥ 3 -point reduction in weekly average of PP-NRS from Baseline to Week 16, defined for the subset of subjects whose baseline NRS is ≥ 3 .
- Proportion of subjects achieving ≥ 4 -point reduction in weekly average of PP-NRS from Baseline to Week 16, defined for the subset of subjects whose baseline NRS is ≥ 4 .

Continuous endpoints will be analyzed using similar method as described above for primary efficacy endpoints, with replacement of each endpoint by EASI in the model; no formal statistical comparison will be performed:

- Change from Baseline to Week 20 in weekly average PP-NRS
- Change in POEM from Baseline to Week 16
- Change in percentage BSA of AD involvement from Baseline to Week 16
- Change in SCORAD from Baseline to Week 16
- Change in DLQI from Baseline to Week 16

AD flares will be recorded as AEs on the eCRF. AD flare related efficacy endpoints will be analyzed using descriptive statistics for each treatment group. Definitions are as follows:

- Number of AD flares from baseline through Week 16

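### AD flares count as TEAEs, so the aggregate AE rows mix disease control with tolerability; flare-excluded rows should be added beside the planned ones

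*SAP*

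**What the plan says.** **How flares are recorded.** Protocol section 7.1.2.3 says that "when an AD flare occurs, its onset and duration will be documented as an AE by the location(s) of flare involvement". SAP section 8.D repeats the rule: "AD flares will be recorded as AEs on the eCRF". It then builds the flare endpoints (number of flares, subjects with flares, days with flare) from those AE records.

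**How TEAEs are counted.** SAP section 9.B gives this definition: "A treatment-emergent AE (TEAE) is defined as any AE that occurs or worsens after initiation of study treatment". Protocol section 11.1.4 runs the treatment-emergent period to the end of follow-up. On the headline table, the SAP says: "An overall summary of AEs will be presented by treatment and overall". It goes on: "The summary will include the total number of events, frequency counts and percentages with" eight rows:
- all AEs;
- TEAEs;
- treatment-emergent SAEs;
- treatment-related TEAEs;
- treatment-related treatment-emergent SAEs;
- TEAEs leading to study drug discontinuation;
- injection site reactions;
- AEs of special interest (ophthalmic).

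Further tables split TEAEs by SOC and preferred term, by maximum severity and by causality. No row or table leaves out flare terms.

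**Expected direction.** Protocol section 13.6.2 says: "It is expected subjects randomized to placebo arm will require TCS medication more often or for longer periods". In the earlier multiple-dose study (Protocol section 5.4.2), AD exacerbation was among the most common AEs, at 26.1% on pooled active and 37.5% on placebo.

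**The concern.** Safety and tolerability by regimen is a secondary objective. The any-TEAE row is the usual first reading of it, and here the row also contains failure to control the disease under study. If a regimen works, its flares fall and its any-TEAE rate falls with them. A similar or lower headline rate on CBP-201 could then coexist with more events of other kinds. The same mechanism could affect comparisons between regimens if they differ in flare control, although the documents give no flare rate by regimen.

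Flares can enter other rows too:
- **Total events.** Flares are documented by location, so one episode could give several AE records. The documents do not say how the eCRF handles this.
- **Related TEAEs.** Protocol section 11.1.1 handles events of unknown causality as related.
- **Discontinuation.** Under Protocol section 7.1.2.3, rescue beyond the permitted topical steroids ends study treatment, so an uncontrolled flare may appear here as intolerance.

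The sponsor has used such aggregates as evidence before. Protocol section 5.4.2 supports its tolerability conclusion partly by noting that the number and severity of TEAEs did not rise with dose.

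**Working it through.** The plan gives no figure for the size of this effect. The only relevant rates are those of the earlier study.

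**1. Reproduce the earlier rates.** The denominators in Protocol section 5.4.2 are 23 active and 8 placebo. 6/23 = 26.1% and 3/8 = 37.5%, matching the text. Exact 95% confidence intervals are about 10% to 48% and 9% to 76%. AEs were reported over the whole 12-week study, of which 4 weeks were treatment.

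**2. Formula.** Let f be the proportion with a flare AE and x the proportion with any non-flare TEAE. The documents give no x, so it is an assumption, set equal in both arms and varied from 20% to 50%. If flares and other TEAEs are independent, any-TEAE = 1 − (1 − f)(1 − x).

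At x = 40%:
- Active: 1 − 0.739 × 0.60 = 55.7%
- Placebo: 1 − 0.625 × 0.60 = 62.5%
- Difference: 6.8 points in favour of active, with no true difference in non-flare events.

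**3. Drop independence.** With maximal overlap, any-TEAE is the larger of f and x. With minimal overlap it is f + x. At x = 40%:
- Maximal: 40.0% in both arms, difference 0.
- Minimal: 66.1% against 77.5%, difference 11.4 points.

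| Assumed x | Maximal overlap | Independence | Minimal overlap |
|---|---|---|---|
| 20% | 11.4 | 9.1 | 11.4 |
| 30% | 7.5 | 8.0 | 11.4 |
| 40% | 0 | 6.8 | 11.4 |
| 50% | 0 | 5.7 | 11.4 |

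Entries are spurious points in favour of active. Heavy overlap removes the effect only when x is at least as high as both flare rates.

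**4. Excess that equal headlines could offset (independence).** Setting the two any-TEAE rates equal gives x(active) = 1 − (1 − 0.375)(1 − x)/0.739. At x = 40% on placebo this is 1 − 0.375/0.739 = 49.3%, an excess of 9.3 points, or about 5 subjects in an arm of 55. Over x = 20% to 50% the excess runs from 12.4 down to 7.7 points.

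**5. Other assumed flare rates (independence, x = 20% to 50%).** With 30% placebo and 20% active, the offset excess is 10.0 down to 6.2 points. With 50% and 25%, it is 26.7 down to 16.7 points.

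**6. Precision.** With 55 per arm, the 95% half-width on the step 2 difference is 1.96 × √(0.557 × 0.443/55 + 0.625 × 0.375/55) ≈ 18 points. The distortion is well inside sampling error, but it is systematic and does not shrink with more subjects.

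**The case against.** A reader might infer that every overall safety row is contaminated and that real drug harms are hidden. The documents do not support that:
- The injection-site and special-interest rows cannot contain AD flares.
- The serious rows contain only flares that meet the seriousness criteria.
- The related rows are partly filtered, because Protocol section 11.1.1 lets events explained by underlying disease be called not related.
- A specific excess would show by preferred term, or in the special-interest, injection-site or laboratory displays.
- SAP section 8.D reports the proportion of subjects with a flare per arm with a confidence interval, so an imbalance would be seen.
- The by-subject AE listing would allow a flare-free count to be derived.

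Recording flares as AEs also follows the protocol's own definition, which includes worsening of a pre-existing abnormality. Safety is descriptive, so no test or decision rule depends on these rows.

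All of this stands, and it limits the reach of the point. It does not close the gap. Preferred-term counts overlap within subjects, so no planned summary table gives the proportion with any TEAE other than a flare. Deriving it later from listings would mean choosing the flare terms after unblinding.

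Two further limits stand. More flare AEs on placebo is an inference: the protocol's statement concerns steroid use, and the earlier study is very small. Flares after dosing stops also count as TEAEs, which may pull the other way in the active arms.

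**Conclusion.** The point holds for the any-AE, any-TEAE and total-event rows and for the SOC row that holds the flare term. It holds to a lesser degree for related TEAEs and TEAEs leading to discontinuation. In those rows an efficacy difference can offset a true excess of other TEAEs.

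The structural point follows from the recording rule and the TEAE definition and needs no assumption. Its size does. The 6.8 points, with a range of 0 to 11.4 by overlap, rest on 6/23 and 3/8, an assumed 40% non-flare rate in both arms, and transfer from a 12-week study to 16 weeks of treatment plus 8 of follow-up. They show that the effect can matter; they do not predict it.

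It might also be inferred that tolerability should be read from flare-excluded rows alone. That goes too far, since it would take genuine worsening on and after drug out of the safety reading. This is a cheap improvement to reporting, not a flaw that invalidates the safety analysis.

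**What to change.** In SAP section 9.B, keep all planned rows and tables. Beside them, add the any-TEAE, total-event, related, discontinuation and severity summaries with AD flare/exacerbation preferred terms excluded, and show flares on their own line. Fix the preferred-term list before unblinding. State that tolerability will be read from the two sets side by side.

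The change needs no new data and alters no clinical rule. The cost is a short term list, some repeated programming and slightly longer AE tables.
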